### **4.3 Study Enrollment Procedures**

4.3.1 *Methods for identifying and recruiting candidates for the trial*

The research team will present SUCCEED to clinicians in the neurology, internal medicine, family medicine, emergency department, and the rehabilitation departments. Study flyers will be posted on the wards, outpatient clinics and housestaff offices of these departments. In the inpatient setting, we will discuss the study with neurology ward nurses and discharge planners, and they will include study flyers in discharge packet. In the outpatient setting, we will discuss the study with the clinic coordinators. Housestaff will be given pocket-sized index cards about the trial. One side of the index card contains a short description of the aim and the eligibility requirements. The back side of the index card contains an IRB-approved short script of a few sentences that describe the study and ask for verbal permission for a member of the research team to approach them to further discuss the study. Finally, contact information of the research team is listed on the card.

We will adapt our highly successful protocol utilized in the SUSTAIN study to identify, approach, and recruit subjects for the SUCCEED study. As stated earlier, a potential subject's clinician need to obtain verbal permission from them before passing their name to a member of the research team.

In the inpatient setting, we have found that embedding the RA within the inpatient team during rounds fosters awareness about the study and prompts the study team during rounds to verbally ask patients for permission for the RA to meet the patient later.

In the outpatient setting, clinicians would notify the site PI, who attends the clinic. The Site PI then contacts the research team RA. Because outpatients may need to leave the clinic immediately after the visit with the clinician, the RA may not be able to speak to outpatients before they leave, but they will be enabled to call the patient at a later time.

Alternatively, potential subjects can also directly call the RA using the toll-free number listed on flyers to learn more about the RCT.

4.3.2 *Procedures (e.g., maintaining a screening log at each clinical site) for documenting how subjects learned about the trial, who referred them to the trial, reasons for ineligibility, and reasons for nonparticipation of eligible subjects.*

Please refer to section 4.3.3 for procedures on consent, documenting how subjects learned about the trial, who referred them to the trial, reasons for ineligibility, documentation of ineligibility, and reasons for nonparticipation of eligible subjects. A description of how this information will be collected centrally and used to enhance subject recruitment efforts is also provided.

4.3.3 *Consent (and assent) procedures*

Interaction between the RA and the potential research subject

- *Arranging initial meeting:* When a clinician notifies the RA a face-to-face meeting will be arranged to check whether the patient meets eligibility criteria for enrollment and to describe elements required for informed consent. The RA will read an IRB-approved script that further describes the SUCCEED trial to the patient.

If a potential subject directly contacts the RA using the toll-free number, the RA will read the IRB-approved script that further describes the SUCCEED trial to the patient. If the potential subject is interested, a face-to-face meeting will be scheduled.

- *Setting:* The consent process will take place in a private room. If the meeting takes place in a shared hospital room, the research staff member will close the curtain when meeting with the participant. The RA will describe the study. RA will be bilingual in English or Spanish, but in the case that a subject speaks a language other than English or Spanish, the research team will use volunteers fluent in the appropriate language to translate for the RA.
- *Eligibility:* If interested in continuing, the RA will ask potential subjects questions about age, and onset of stroke to confirm eligibility. They will also take BP measurements. Finally, they will ask questions that require comprehending the basics details of the study. If participants cannot describe what is told to them, they will not be enrolled in SUCCEED. For potential subjects found to be ineligible, the reasons for ineligibility will be recorded.
- *Voluntary consent:* The RA will ensure that eligible subjects are given every opportunity ask questions, and remind the patients that participation in SUCCEED is voluntary. If interested, the potential subject will sign the written consent form. Potential participants will have the opportunity to take the consent document home and discuss participation with others before making a decision.
- *Declining consent:* If patients do not consent to the study, the RA will record the reason why the patient did not consent. Further, the RA will ask permission to use the demographic information of the patient to generate enrollment propensity weights. Enrollment propensity weights will be used to analyze how the tendency to participate in the RCT impacts attainment of outcomes.
- *Storing consent forms.* The consent forms at each site will be stored in a locked file cabinet within a locked room. Access is limited to the site's Principal Investigator and research staff.

For the baseline survey, the RA will enter the circumstances of the initial visit (inpatient/outpatient, whether clinical team called RA or subject, reasons for ineligibility, and reasons for nonparticipation). These data will be summarized in a monthly report by site and shared among the Task Force and the research teams at UCLA and at each site.

#### 4.3.4 *Procedure for obtaining intervention group assignment*

Before the RCT begins, we will use computer-assisted stratified randomization of block size of 4. The three stratification variables will be site, spoken language (Spanish, English or other), and type of stroke (ischemic or hemorrhagic). These lists have an allocation ratio of 1:1 of control and intervention. Permuted block randomization that stratifies by site will be used to promote periodic balance through the trial and group balance at the end of the trial. The study programmer/analyst will generate 24 lists, one for each stratum. Each row of the list will include a unique subject IDs and intervention arm of the study. The lists will be kept in a notebook that the Project Coordinator will possess at all times.

For patients who consent to the study and meet inclusion criteria, the RA will collect baseline data (described below in section of Outcome Measures) before randomization so that the RA will collect data uniformly regardless of the eventual allocation of the subject. After an eligible participant has consented and completed the baseline survey, the RA will inform the Project Coordinator with the information needed to choose which of the 24 lists to use. The Project Coordinator will find the next uncrossed row, tell the RA the unique subject ID and intervention assignment, then cross out that row so that the next row will be used when this list is used again.

The Project Coordinator will assign the newly enrolled participant a unique subject ID and inform the RA the assigned randomization status of this subject. The Project Coordinator will mark down in the notebook the date of randomization for that subject ID.

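### A single published block size of 4, with the recruiting RA told every assignment, can let that RA foresee up to one third of allocations before consent and baseline BP

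*Combined protocol and SAP*

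**What the plan says.** Section 4.3.4 sets the scheme: "we will use computer-assisted stratified randomization of block size of 4". It adds: "These lists have an allocation ratio of 1:1 of control and intervention". On the strata: "The study programmer/analyst will generate 24 lists, one for each stratum". Only one block size is given, and nothing says it is withheld from site staff.

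On custody: "The lists will be kept in a notebook that the Project Coordinator will possess at all times". Once a participant has consented and finished the baseline survey, the coordinator takes the next unused row and must "tell the RA the unique subject ID and intervention assignment, then cross out that row". The order of steps is deliberate: "the RA will collect baseline data (described below in section of Outcome Measures) before randomization".

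Section 4.3.3 gives the RA the face-to-face meeting, the eligibility questions, the BP measurement, the consent discussion and a comprehension check: "If participants cannot describe what is told to them, they will not be enrolled in SUCCEED". Table 3 and section 4.2.6 exclude SBP below 120 mm Hg. (Section 4.2.2 prints the opposite sign and must be reconciled with them; this point does not depend on it.) Section 6.2.1 puts screening, baseline and randomization in one encounter. Sections 3 and 9.1 promise a blinded RA, but for outcome assessment.

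**The concern.** Holding the list in a notebook hides the list. It does not hide what past assignments reveal. The comparison is care-manager and community-health-worker care against usual care, so each arm is plain once it is told. A recruiter who knows that every block holds two of each arm can count. The fourth place is always determined, and so is the third whenever the first two match.

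Collecting baseline data before randomization protects uniformity only if the RA cannot already work out the next arm. A separate blinded assessor at follow-up would not help, because the exposure comes earlier: in whom to approach and when, in the comprehension judgement, and in the reading used both for the SBP cut-off and as baseline for the primary outcome. The order of enrollment can be shifted, since onset may be up to three months back (Table 3), outpatients may be called later (4.3.1) and patients may take the consent form home (4.3.3). At stake is the comparability of the arms at entry.

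**Working it through.** **Inputs.** Block size 4, ratio 1:1, 24 lists (4.3.4); 500 participants (Synopsis). The plan's only figure for the scheme reproduces: 4 sites × 3 languages × 2 stroke types = 24. It gives no predictability figure.

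**Certain knowledge, complete blocks.** There are 6 possible orders of two control and two intervention places. The chance that each place is known in advance is:
- places 1 and 2: 0
- place 3: 1/3 (the first two match in 2 of 6 orders)
- place 4: 1

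Mean = (0 + 0 + 1/3 + 1)/4 = 1/3, and 500/3 = 167.

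**Unfinished last blocks.** Simulating 500 participants over the 24 strata, with the 2011 site and stroke-type shares of Table 2 and assumed language mixes, gave 31.5% (95% of runs between about 29% and 34%), about 157 of 500. The language mix hardly changed this.

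**Best guess.** Always naming the arm with more places left is right with probability 1/2, 2/3, 2/3 and 1 at the four places. Sum = 2.83; 2.83/4 = 70.8%, against 50% with no information. With 21 per stratum, so that one block is unfinished, it is 69.9%.

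**Several RAs per stratum (assumption).** Suppose k RAs split a stratum at random and share nothing, but each still knows where blocks begin. The RA must have enrolled both participants of the exhausted arm personally, which has probability 1/k². Certain knowledge becomes (1/3)/k²:
- k = 1: 33.3%
- k = 2: 1/12 = 8.3% (7.8% with unfinished blocks)
- k = 3: 1/27 = 3.7% (3.5% with unfinished blocks)

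**Alternatives, for one RA who hears everything and knows the possible sizes.** The mixed-size rows are simulated at 20 to 21 per stratum with an optimal guesser; the single-size rows are exact for complete blocks.

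| Block sizes | Known for certain | Best guess right |
|---|---|---|
| 4 | 33.3% | 70.8% |
| 6 only | 25% | 68.3% |
| 8 only | 20% | 66.6% |
| 4 and 6, random | about 6% | about 68–69% |
| 4, 6 and 8, random | about 2.4% | about 67% |

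A larger single block, once known, still leaves a fifth to a quarter determined. Varying the size removes most of the certainty but only 2 to 4 points of guessing accuracy.

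**The case against.** The strongest reply is that one third is a ceiling. It needs an RA who knows the block size and hears every assignment in the stratum. The documents do not give the number of RAs per site and speak of them in the plural (4.3.4, 6.3.7). That RAs have read the block size is an inference from its being printed in the protocol. This stands, and the figure must carry its condition. But site is a stratification factor, so one RA per site meets the second condition, and nothing stops RAs from sharing assignments.

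Discretion is also limited. Section 6.3.7 requires five minutes seated, an automatic device, two readings, two more if they differ by over 5 mm Hg, and an average computed by the data system. Candidates come by clinician referral or call in themselves, the approach is scripted, and reasons for ineligibility and refusal are logged and reviewed (4.3.1, 4.3.3, 4.3.4). These measures reduce the scope for selection; they do not remove the comprehension judgement or the timing of approach.

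A reader might infer that a known number of mm Hg of bias enters the 8 mm Hg hypothesized effect. The documents do not support that. Any figure would rest on an assumed distortion among the predictable assignments, and on how far the covariate-adjusted analyses of section 9.5 absorb a true baseline difference. Nor do they show that any RA would act on a prediction.

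Small blocks also serve a stated aim, balance during the trial, and some strata are tiny: Table 2 shows 4 to 8 hemorrhagic strokes a year at Olive View, to be divided among three language groups.

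**Conclusion.** The concern holds as a weakness in allocation concealment, conditional on what the RA knows. Between about 31% and 33% of assignments are foreseeable with certainty by one RA who knows the block size and hears every assignment in a stratum. The figure is about 8% with two non-sharing RAs per stratum and 3 to 4% with three. Neither the notebook, the baseline-first order nor the blinded outcome assessor prevents the deduction. This is an opportunity for selection, not evidence of it, and the documents do not allow the resulting bias in SBP to be calculated. It merits a change because the change is cheap, not because the primary comparison has been shown to be biased.

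**What to change.** In section 4.3.4, replace the single block size with randomly varying sizes within the same 24 strata, generated by the study programmer. State in the protocol only that sizes vary; keep the sizes in a restricted document and do not disclose them to RAs. The Project Coordinator can go on holding the lists and releasing the next row, so no new custodian is needed.

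Section 4.3.4 already places consent and the baseline survey before assignment. Add that eligibility and baseline BP must be entered and submitted before the arm is released. Section 10.2.1 says submitted data are no longer available to the site, so submission acts as the lock. Because the subject ID now arrives together with the arm, either a screening number is needed or the ID must be released before the arm.

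Cost: 24 regenerated lists, a few sentences in 4.3.4 and that small procedural step. The statistical price is slightly more possible imbalance. The largest difference between arms within an open block is half its size: 2 with blocks of 4, 3 with blocks of 6 and 4 with blocks of 8. Where strata are tiny this favors sizes 4 and 6. Since guessing stays near 67 to 69% even with mixed sizes, the submission step and the non-disclosure matter as much as the block sizes.

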### 3 STUDY DESIGN

**Figure 1. SUCCEED Study Design**

The study design for SUCCEED trial is a multi-center, randomized controlled trial of a Care Management and Community Health Worker led intervention VS Usual Care to improve management of stroke risk factors. The outcomes of this study will be assessed by a blinded Research Assistant. Subjects will be enrolled in the RCT for a period of 1 Year. A diagram of the study is provided as shown in **Figure 1 to the left**.

We designate systolic blood pressure as the primary outcome for the purpose of sample size calculations. We will assess multiple relevant outcomes including all risk factors and a composite index, cost, quality of life, adverse consequences, moderators, mediators, and a range of metrics of intervention program implementation and participation.

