#### Efficiency and productivity metrics such as tracking the effectiveness and outcomes of recruitment strategies employed

We have the data to determine the enrollment ratios.

- Numerator: we have developed tracking databases for the RAs to record the number of approached patients per month. They further document the reason for ineligibility among subjects. For eligible subjects, the RAs further document which patients consent or decline to participate, and for those that decline, the reasons for not participating.
- Denominator: On a periodic basis, administrators at the LAC-DHS run reports for the SUSTAIN team that show the number of patients hospitalized at each site per month.

Using our tracking databases and the LAC-DHS reports, we can calculate the proportion of hospitalized stroke patients approached by our research team and the proportion of eligible stroke patients who consent to participate in the study. This will allow us to discern when and where and why study enrollment rates are lower than expected.

These enrollment statistics will be shared among the research team and the Task Force. If rates of participating are lower than expected at a site, we will investigate the reasons for doing so and develop strategies for overcoming barriers. This feedback loop has been critical for developing our successfully recruitment strategy in SUSTAIN.

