## 5 STUDY INTERVENTIONS

### 5.1 Interventions, Administration, and Duration

The intervention team consists of the following:

- Care Managers
- Community Health Workers
- Research Assistants

The intervention is:

- Care by CM
- Medical algorithms
- Report cards

Community Health worker home visits and community self management classes, supported by mobile technology.

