## 9 STATISTICAL CONSIDERATIONS

### 9.1 General Design Issues

The primary and secondary hypotheses is that subjects randomized to the intervention arm will have better control of risk factors and higher rates of adoption of healthy lifestyle habits compared to the control arm.

All outcomes will be collected by a blinded RA. Vascular events will be collected by patient self-report and will not require an adjudication committee.

The design is a RCT, 1:1 allocation to control and intervention arms. There is no crossover.

Randomization is stratified by site (4), language (3: English, Spanish, other), and type of stroke (2: ischemic/TIA, hemorrhagic). There are 24 strata.

Intervention on period is up to 12 months for persons. It may be discontinued if subjects optimally control risk factors.

After the 12 month study period, subjects will be monitored by telephone for the presence of vascular events and mortality. There is no face-to-face contact, and thus, no collection of SBP, the primary endpoint. This surveillance is to better determine the impact of the intervention in the first 12 months after randomization.

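### The plan promises blinded outcome assessment, but Section 4.3.4 has the RA told each subject's arm and nothing separates that RA from the one who does the subject's follow-up

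*Combined protocol and SAP*

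**What the plan says.** Blinding is promised in three places. The Synopsis (Design and Outcomes) and Section 3 both state: "The outcomes of this study will be assessed by a blinded Research Assistant". Section 9.1 is broader: "All outcomes will be collected by a blinded RA".

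Section 4.3.4 describes how the arm is disclosed. After consent and the baseline survey, the Project Coordinator finds the next unused row of the stratum's list and is to "tell the RA the unique subject ID and intervention assignment". The following paragraph again has the Coordinator "inform the RA the assigned randomization status of this subject". Baseline data are collected before this step, so that knowledge of the arm cannot influence them.

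Other sections give the RA further duties under the same title:
- Section 4.3.3: eligibility and consent, including blood pressure ("They will also take BP measurements").
- Section 6.3.7: certification in the NIHSS and modified Rankin scale.
- Section 10.2.1: entry of examination, survey and laboratory results.

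There is more than one RA. The recruitment-metrics text in Section 4.3 says "we have developed tracking databases for the RAs to record the number of approached patients per month". In Section 5.1, the list that opens "The intervention team consists of the following" includes Research Assistants, but no intervention task is given to them. On events, Section 9.1 adds: "Vascular events will be collected by patient self-report and will not require an adjudication committee".

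**The concern.** The intervention is care management, home visits and classes, so patients and care teams will know the arm. The outcome assessor is the only blinded party that the plan names. If the RA who was told the arm returns at 3 or 12 months, that protection is lost for that subject, and following Section 4.3.4 to the letter makes this possible.

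An assessor who knows the arm can influence how questions are asked, how answers are probed and how readily an event is recorded. Such an influence cannot be removed afterwards. Because the plan asks for no record of unblinding, a later report could not show how far the blind was kept.

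**Working it through.** **1. The statements side by side.** Section 9.1 requires that whoever collects an outcome is unaware of the arm. Section 4.3.4 makes an RA aware of it, for every subject, at enrolment. The two are compatible only if that RA does not collect that subject's later outcomes.

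**2. Is that separation stated?** The places where it could appear are Sections 4.3.3, 4.3.4, 5.1, 6.2, 6.3.7, 9.1 and 10.2.1. None reserves an RA for follow-up or bars the enrolling RA from it. Section 6.3.7 certifies every RA for the rating scales and sets no blinded group apart. Section 6.2.5 says the 12-month visit follows the baseline and 3-month pattern, without randomization, and names no separate assessor. Section 10.4 cites the Manual of Operations only for adverse experiences.

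**3. How could a follow-up RA learn the arm?**
- *Written sources:* limited. The lists stay in the Coordinator's notebook (4.3.4). The linking file is described as holding name, address, phone number and subject ID, not arm (10.1). Submitted data are no longer available at the site (10.2.1). An RA who did not enrol the subject therefore has no described written source.
- *Having been told at enrolment:* open for the enrolling RA.
- *From the patient:* open. No passage asks patients to withhold their arm or has the RA record it if they do not.

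**4. Which outcomes are exposed?** Baseline is unaffected. After randomization:

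| Outcome | Protection in the plan | Exposure |
|---|---|---|
| Lifestyle behaviours (Table 1) and other questionnaire measures | None described. Section 6.3.12 does not list the lifestyle items; I assume they are asked by an RA | Highest |
| Vascular events | Self-report without adjudication (9.1), but stroke and myocardial infarction are also sought in administrative databases (6.3.2, 6.3.3) | High, partly backed |
| Systolic blood pressure (SBP) | OMRON device, 5-minute rest, fixed repeat rule, average computed by the system (6.3.7); staff still choose the cuff and position the arm | Partial |
| Lipids, HbA1c, CRP | Meter reading or blood-spot assay (6.3.8) | Little |
| Death | Hard endpoint, also in administrative databases | Little |

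For the telephone surveillance after 12 months, Section 6.2.5 does not say who makes the calls. It is exposed only if RAs do.

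**5. Scale.** Section 9.3 gives 2.6 and 2.4 data points per subject. These reproduce as one baseline plus two follow-up visits at the stated attrition: 1 + 2 × 0.8 = 2.6 and 1 + 2 × 0.7 = 2.4. Removing the baseline leaves 1.6 and 1.4. Over 500 subjects:
- 20% attrition: 500 × 1.6 = 800 SBP visit values at 3 and 12 months.
- 30% attrition: 500 × 1.4 = 700.

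This counts the values that rely on the assessor. It does not count those that would be unblinded. The documents give neither that share nor the bias an unblinded RA would introduce, so no effect on the type I error or the estimate can be derived.

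**The case against.** The strongest reply is that nothing here is a flat contradiction. RAs are plural, so the sponsor may intend one to enrol and another to assess. The only assignment record described stays with the Coordinator. All of that stands. It limits the point to a missing rule; it does not supply the rule, because an unstated intention does not bind four sites.

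A second reply is that the primary outcome is largely machine-read. This also stands in part: the device, repeat rule and computed average leave the assessor little room, though they do not replace blinding. The administrative databases likewise give stroke, myocardial infarction and death a source independent of the RA.

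Three stronger readings are tempting, and the documents do not support them:
- *Follow-up will be unblinded.* No passage says that the enrolling RA does the follow-up.
- *RAs deliver the intervention because Section 5.1 lists them on the team.* The section gives them no intervention task. It needs clarifying but proves nothing.
- *The NIHSS and Rankin are the badly exposed endpoints because they are rater-scored.* They are scheduled examinations, but neither is in Table 1, the list of primary and secondary outcomes.

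**Conclusion.** The concern holds in limited form and should be fixed. The plan promises blinded assessment in three places and instructs disclosure of the arm to the RA twice. It has no provision that keeps an RA who was told the arm away from that subject's follow-up. Confidence in this is high, because it rests on the text alone.

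The weight falls mainly on interview-based outcomes and self-reported events, less on SBP, and little on laboratory values and death. A reader might infer an inflated false-positive rate for SBP. Any such figure would need an assumed bias and an assumed share of unblinded visits, neither of which the documents provide, so I give none. The conclusion assumes that no separation rule exists outside the documents. If one does, for example in the Manual of Operations, it need only be moved into Section 9.1.

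**What to change.** 1. **Section 4.3.4, both sentences.** The Coordinator gives an RA who will assess the subject only a subject ID, and the ID must not encode the arm. The assignment goes to the patient and, for intervention patients, to the Care Manager through a staff member who does not assess that subject. This can happen at the same encounter, after the Coordinator has crossed out the row, so no assignments need be prepared in advance and held at sites. Alternatively, the enrolling RA may be told the arm if a different existing RA does all of that subject's follow-up.
2. **Section 9.1.** Add that no RA who knows a subject's assignment collects that subject's follow-up outcomes, that patients are asked not to reveal their arm, and that the RA records at each contact whether the arm became known.
3. **Section 5.1.** State that outcome-assessing RAs deliver no intervention, or remove them from the team list.

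The cost is protocol wording, one item on each follow-up form, a small hand-off task at randomization, and rostering among existing RAs. The documents do not give the number of RAs per site; a site with only one would need cover from another. Sample size, visit schedule and clinical care are unchanged.
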